9.8. Interim Analysis

No formal interim analysis is planned for this study.

9.9. Other Topics

9.9.1. Analysis of Exploratory Endpoints

Exploratory analyses will be conducted on the exploratory efficacy endpoints listed in Section 2. Exploratory efficacy endpoints will be summarized using descriptive statistics by treatment group. For continuous endpoints, number of subjects (n), mean, SD, SE, median, minimum, and maximum will be provided. Binary endpoints will be summarized by number and percentages.

9.9.2. Pharmacokinetics, Pharmacodynamics and Exposure-Response

Serum trough concentrations (C_{trough}) of CC-93538 will be summarized with descriptive statistics by treatment and visit. Additional analysis may be conducted as appropriate (eg, by ADA status).

Population PK analysis will be performed using nonlinear mixed-effects modeling to characterize the population PK of CC-93538 and to identify key covariate effects (eg, immunogenicity, intrinsic and extrinsic factors). Data from other studies may be included if appropriate. Exposure-response and pharmacodynamic relationships will be conducted for efficacy, safety, and biomarker endpoints. Details on the studies and methodology will be outlined in a separate PK Analysis Plan, and results will be issued separately from the clinical study report as a stand-alone report.

9.9.3. Data Monitoring Committee

Additional safety monitoring will be performed by an external, independent Data Monitoring Committee (DMC). A DMC will be convened that will include physicians with experience in treating subjects with type 2 inflammatory diseases, as well as a statistician, all of whom are not otherwise involved in the study conduct and for whom there is no identified conflict of interest.

During the study, the DMC will review selected data (to be specified in the DMC charter) on a regular basis for the assessment of benefit-risk and determination of study continuation. An independent third party will prepare the reports of aggregate data summaries and individual subject data listings, as appropriate, for the DMC members for each scheduled meeting. Operational details for the DMC, including a blinding plan to assure that all personnel involved in the conduct of the study remain blinded to the results of data reviews, will also be described in the DMC charter. The DMC will function in advisory capacity, making recommendations based on their independent assessment of the safety data. Unblinded safety data may be reviewed on a periodic or ad-hoc basis by the DMC, as needed, to further enhance the ongoing assessment of the risk/benefit of the IP.

10. ADVERSE EVENTS

10.1. Monitoring, Recording and Reporting of Adverse Events

An AE is any noxious, unintended, or untoward medical occurrence that may appear or worsen in a subject during the course of a study. It may be a new intercurrent illness, a worsening concomitant illness, an injury, or any concomitant impairment of the subject's health, including laboratory test values (as specified by the criteria in Section 10.3), regardless of etiology. Any worsening (ie, any clinically significant adverse change in the frequency or intensity of a preexisting condition) should be considered an AE. A diagnosis or syndrome should be recorded on the AE page of the CRF rather than the individual signs or symptoms of the diagnosis or syndrome.

Abuse, withdrawal, sensitivity or toxicity to an investigational product should be reported as an AE. Overdose, accidental or intentional, whether or not it is associated with an AE should be reported on the overdose CRF. (See Section 7.2.3 for the definition of overdose). Any sequela of an accidental or intentional overdose of an investigational product which meets the definition of an adverse event, should be reported as an AE on the CRF. If the sequela of an overdose meets serious criteria, then it must be marked as serious on the CRF. The overdose itself should not be reported as an AE.

In the event of overdose, the subject should be monitored as appropriate and should receive supportive measures as necessary. There is no known specific antidote for CC-93538 overdose. Actual treatment should depend on the severity of the clinical situation and the judgment and experience of the treating physician.

All subjects will be monitored for AEs during the study. Assessments may include monitoring of any or all of the following parameters: the subject's clinical symptoms, laboratory, pathological, radiological or surgical findings, physical examination findings, or findings from other tests and/or procedures.

All AEs will be recorded by the Investigator from the time the subject signs informed consent until 16 weeks after the last dose of IP, or the last Follow Up visit, whichever is longer, as well as those SAEs made known to the Investigator at any time thereafter that are suspected of being related to IP. All AEs (serious/non-serious) will be recorded on the CRF and in the subject's source documents. Refer to Section 10.5 for instructions on how to report SAEs to Drug Safety.

10.2. Evaluation of Adverse Events

A qualified Investigator will evaluate all adverse events as to:

10.2.1. Seriousness

An SAE is any AE occurring at any dose that:

- Results in death;
- Is life-threatening (ie, in the opinion of the Investigator, the subject is at immediate risk of death from the AE);

- Requires inpatient hospitalization or prolongation of existing hospitalization (hospitalization is defined as an inpatient admission, regardless of length of stay);
- Results in persistent or significant disability/incapacity (a substantial disruption of the subject's ability to conduct normal life functions);
- Is a congenital anomaly/birth defect;
- Constitutes an important medical event.

Important medical events are defined as those occurrences that may not be immediately lifethreatening or result in death, hospitalization, or disability, but may jeopardize the subject or require medical or surgical intervention to prevent one of the other outcomes listed above. Medical and scientific judgment should be exercised in deciding whether such an AE should be considered serious.

Events not considered to be SAEs are hospitalizations for:

- a procedure that is planned (ie, planned prior to start of treatment on study); must be documented in the source document and the CRF. Hospitalization or prolonged hospitalization for a complication remains a reportable SAE.
- an elective treatment of or an elective procedure for a pre-existing condition, unrelated to the studied indication, that has not worsened from baseline.
- emergency outpatient treatment or observation that does not result in admission, unless fulfilling other seriousness criteria above.

For each AE, the Investigator will provide information on severity, start and stop dates, relationship to the IP, action taken regarding the IP, and outcome.

10.2.2. Severity/Intensity

For each AE, the Investigator must assess the severity/intensity of the event.

The following grading scale should be used to evaluate severity/intensity:

Mild

- Asymptomatic or mild symptoms; clinical or diagnostic observations only
- Intervention not indicated
- Activities of daily life (ADLs) minimally or not affected
- No or minimal intervention/therapy may be required

Moderate

- Symptom(s) cause moderate discomfort
- Local or noninvasive intervention indicated
- More than minimal interference with ADLs but able to carry out daily social and functional activities
- Drug therapy may be required

Severe (could be non-serious or serious)

- Symptoms causing severe discomfort/pain
- Symptoms requiring medical/surgical attention/intervention
- Interference with ADLs including inability to perform daily social and functional activities (eg, absenteeism and/or bed rest)
- Drug therapy is required

The term "severe" is often used to describe the intensity of a specific event (as in mild, moderate or severe myocardial infarction); the event itself, however, may be of relatively minor medical significance (such as severe headache). This criterion is *not* the same as "serious" which is based on subject/event *outcome* or *action* criteria associated with events that pose a threat to a subject's life or functioning.

Seriousness, not severity, serves as a guide for defining regulatory obligations.

10.2.3. Causality

The Investigator must determine the relationship between the administration of the IP and the occurrence of an AE as Not Suspected or Suspected as defined below:

Not suspected:	a causal relationship of the adverse event to IP administration is unlikely or remote , or other medications, therapeutic interventions, or underlying conditions provide a sufficient explanation for the observed event.
Suspected:	there is a reasonable possibility that the administration of IP caused the adverse event. 'Reasonable possibility' means there is evidence to suggest a causal relationship between the IP and the adverse event.

Causality should be assessed and provided for each AE based on currently available information. Causality is to be reassessed and provided as additional information becomes available.

If an event is assessed as suspected of being related to a comparator, ancillary or additional IP that has not been manufactured or provided by Celgene, please provide the name of the manufacturer when reporting the event.

10.2.4. Duration

For each AE, the Investigator will provide a record of the start and stop dates of the event.

10.2.5. Action Taken

The Investigator will report the action taken with IP as a result of each AE, as applicable (eg, discontinuation, interruption, or dose reduction of IP, as appropriate) and report if concomitant and/or additional treatments were given for the event.

10.2.6. Outcome

The Investigator will report the outcome of the event for each AE.

All SAEs that have not resolved upon discontinuation of the subject's participation in the study must be followed until recovered (returned to baseline), recovered with sequelae, or death (due to the SAE).

10.3. Abnormal Laboratory Values

An abnormal laboratory value is considered to be an AE if the abnormality:

- results in discontinuation from the study;
- requires treatment, modification/ interruption of IP dose, or any other therapeutic intervention; or
- is judged to be of significant clinical importance, eg, one that indicates a new disease process and/or organ toxicity or is an exacerbation or worsening of an existing condition.

Regardless of severity grade, only laboratory abnormalities that fulfill a seriousness criterion need to be documented as a serious adverse event.

If a laboratory abnormality is one component of a diagnosis or syndrome, then only the diagnosis or syndrome should be recorded as the AE. If the abnormality was not a part of a diagnosis or syndrome, then the laboratory abnormality should be recorded as the AE. If possible, the laboratory abnormality should be recorded as a medical term and not simply as an abnormal laboratory result (eg, record thrombocytopenia rather than decreased platelets).

10.4. Pregnancy

All pregnancies or suspected pregnancies occurring in either a female subject of childbearing potential or partner of childbearing potential of a male subject are immediately reportable events.

10.4.1. Females of Childbearing Potential

Pregnancies and suspected pregnancies (including elevated β -hCG or positive pregnancy test in a female subject of childbearing potential regardless of disease state) occurring while the subject is on IP, or within 5 months of the subject's last dose of IP are considered immediately reportable events. Investigational product is to be discontinued immediately. The pregnancy, suspected pregnancy, or positive pregnancy test must be reported to Celgene Drug Safety immediately by email, phone or facsimile, or other appropriate method, using the Pregnancy Initial Report Form, or approved equivalent form.

The female subject may be referred to an obstetrician-gynecologist or another appropriate healthcare professional for further evaluation.

The Investigator will follow the female subject until completion of the pregnancy and must notify Celgene Drug Safety immediately about the outcome of the pregnancy (either normal or abnormal outcome) using the Pregnancy Follow-up Report Form or approved equivalent form. If the outcome of the pregnancy was abnormal (eg, spontaneous abortion), the Investigator should report the abnormal outcome as an AE. If the abnormal outcome meets any of the serious criteria, it must be reported as an SAE to Celgene Drug Safety within 24 hours of the Investigator's knowledge of the event.

All neonatal deaths that occur within 28 days of birth should be reported, without regard to causality, as an SAE. In addition, any infant death after 28 days that the Investigator suspects is related to the in utero exposure to the IP should also be reported as an SAE to Celgene Drug Safety within 24 hours of the Investigator's knowledge of the event.

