3.2. Study Duration for Subjects

The maximum duration of subject participation in this study is approximately 36 weeks. Subjects will participate up to 4 weeks in the Screening Period. Upon randomization, subjects will enter the Treatment Phase of the study, and will receive a total of 16 doses of IP starting at Day 1 (Baseline) and ending at Week 15.

At Week 16, subjects will return for the End of Treatment Visit for safety and efficacy assessments. Following the Week 16 End of Treatment Visit, subjects will enter a 16 Week Follow Up Period, and will return for 2 additional visits to assess safety, clinical status, PK/PD, and serum antibodies to CC-93538. The Initial Follow Up Visit will be conducted 8 weeks after
the End of Treatment Visit (Week 24) and the Final Follow Up/End of Study Visit will be conducted 16 weeks after the End of Treatment Visit (Week 32).

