- 7. Subjects currently receiving concomitant medications for any reason other than AD, such as inhaled corticosteroids, leukotriene receptor antagonists (eg, montelukast), or mast cell stabilizers (eg, cromolyn sodium) for asthma, must be on a stable regimen, which is defined as not starting a new drug, changing, or stopping dosage within 7 days or 5 half-lives (whichever is longer) prior to Day 1 and through the treatment duration of the study.

- 8. Female subjects of childbearing potential must agree to practice a highly effective method of contraception. Highly effective methods of contraception are those that alone or in combination result in a failure rate of a Pearl index of less than 1% per year when used consistently and correctly. A female of childbearing potential (FCBP) is a female who: 1) has achieved menarche at some point, 2) has not undergone a hysterectomy or bilateral oophorectomy, or 3) has not been naturally postmenopausal (amenorrhea following cancer therapy does not rule out childbearing potential) for at least 24 consecutive months (ie, has had menses at any time in the preceding 24 consecutive months) and must:
 - a. Have two negative pregnancy tests as verified by the Investigator prior to starting study therapy. She must agree to ongoing pregnancy testing during the course of the study and through the Final Follow-up Visit. This applies even if the subject practices true abstinence* from heterosexual contact.
 - b. Either commit to true abstinence* from heterosexual contact (which must be reviewed on a monthly basis and source documented) or agree to use, and be able to comply with, highly effective contraception without interruption throughout the study and for 5 months after the last dose of IP.

Acceptable methods of birth control in this study are the following:

- a. combined hormonal (estrogen and progestogen containing) contraception, which may be oral, intravaginal, or transdermal Note: Intravaginal and transdermal combined hormonal contraception are not approved by Japan Health Authority and would therefore not be acceptable methods contraception for subjects enrolled in this region.
- b. progestogen-only hormonal contraception associated with inhibition of ovulation, which may be oral, injectable, or implantable.
 Note: progestogen-only hormonal contraception is not approved by Japan Health Authority and would therefore not be acceptable methods contraception for subjects enrolled in this region.

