- ^j Starting at Week 3, subjects may have the option to return to the clinic every other week for IP administration, and have their alternate week injections administered at home by a visiting home health nurse. Subjects who utilize the home health nurse option will be required to return to the site every 2 weeks at a minimum (eg, Week 4 [Visit 5/Day 29], Week 6 [Visit 7/Day 43], Week 8 [Visit 9/Day 57], Week 10 [Visit 11/Day 71], Week 12 [Visit 13/Day85], Week 14 [Visit 15/Day 99], and Week 16 [Visit 17/Day 113]) during the treatment phase of study for scheduled laboratory collections, and additional safety and efficacy assessments. In addition, on the weeks that the IP is not administered inclinic, the subject will be contacted by site personnel (within 24 hours) to assess for any changes in concomitant medication use and assess for adverse events.
- ^k Subjects for whom home health nurse services are not available in their region, or who choose not to utilize the visit home health nurse service option, will be required return to the clinic weekly for their injections.

Study Procedure	Follow-Up	(FU) Period	
Visit Label	Initial Follow Up Visit 18 (Week 24)	Final Follow Up/ End of Study (EOS) Visit 19 (Week 32)	Additional Notes (if applicable)
Visit Timing (Visit Window)	End of Treatment (EOT) Visit +8 Weeks (±7 day)	EOT Visit Last Dose +16 Weeks (±7 day)	All visits conducted during the Follow Up Period are onsite visits.
Concomitant therapy	Х	Х	Refer to Section 8 for additional guidance.
Adverse Events (AEs)/Serious Adverse Events (SAEs)	X	Х	Refer to Section 10 for additional guidance on AE/SAE collection.
Hematology and chemistry	Х	Х	Refer to Section 6.1 and Section 6.1.1 for
Urinalysis	X	Х	additional guidance on the collection of safety laboratory samples.
Urine (or serum) pregnancy test (female of child-bearing potential only)	X	Х	At each study visit, the Investigator will counsel female of child-bearing potential (FCBP) subjects on pregnancy precautions for the duration of the study
Physical exam (complete)	X	Х	A complete physical examination includes an evaluation of heart, lung, head and neck, abdomen, neurological assessment, and extremities.
Vital signs	X	X	Vital signs: Heart rate, blood pressure (systolic and diastolic), respiratory rate, and temperature will be assessed at each visit. Blood pressure and pulse will be assessed in a sitting position and once the subject is at rest. An automated validated device may be used, if available.

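### Contraception and pregnancy reporting run to 5 months after the last dose, but the last scheduled pregnancy test and contact fall 17 weeks after it, leaving about a month without planned ascertainment

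*Combined protocol and SAP*

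**What the plan says.** Two post-dose obligations share one length. Section 10.4.1 covers pregnancies and suspected pregnancies on IP "or within 5 months of the subject's last dose of IP are considered immediately reportable events". Section 4.2, criterion 8b, asks women of childbearing potential either to commit to true abstinence or to use "highly effective contraception without interruption throughout the study and for 5 months after the last dose of IP". For those relying on abstinence, the criterion adds a review "which must be reviewed on a monthly basis and source documented".

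Scheduled ascertainment has a different length. Criterion 8a states: "She must agree to ongoing pregnancy testing during the course of the study and through the Final Follow-up Visit". Section 3.2 says that subjects "will receive a total of 16 doses of IP starting at Day 1 (Baseline) and ending at Week 15", with the End of Treatment (EOT) visit at Week 16 and follow-up visits at Weeks 24 and 32, the latter also being End of Study. Table 5 places pregnancy tests and counselling at those two visits and lists nothing later. Its header for the final visit names both the EOT visit and the last dose as the start of the 16 weeks, with a window of 7 days either way. Under Section 6.3.1, a subject who leaves early has her 16 weeks of follow-up counted from the last treatment-phase visit, for example the Early Termination (ET) visit. Section 10.1 closes adverse event recording at 16 weeks after the last dose or at the last follow-up visit, whichever is later; after that, only serious events suspected of being related to IP are collected.

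**The concern.** The sponsor has chosen 5 months as the period over which a pregnancy after exposure is of interest, both for prevention and for reporting. The visit schedule does not reach the end of that period. A site that follows the protocol exactly has no planned occasion to learn of a pregnancy that begins after the Week 32 test, although such a pregnancy may still be immediately reportable.

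This matters because Section 10.4.1 builds on that knowledge: the investigator follows each pregnancy to completion and records an abnormal outcome as an adverse event. Those steps can start only once the site knows. Section 1.2.2.4 reports one severe, possibly related spontaneous abortion in the open-label extension of the earlier Phase 2 study, so the outcome is not hypothetical in this programme.

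A smaller problem lies inside follow-up. The monthly review of abstinence has no scheduled contact to carry it between Weeks 16, 24 and 32.

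**Working it through.** **Inputs**

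- Last planned dose: Week 15, Day 106 (Section 3.2; Table 4).
- EOT visit: Week 16, Day 113 (Table 4).
- Final visit: 16 weeks after EOT, window 7 days either way (Section 3.2; Table 5).
- Reporting and contraception window: 5 months after the last dose (Section 10.4.1; criterion 8b). The protocol does not define a month in days.

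**The plan's own duration, reproduced.** 4 weeks screening + 16 weeks treatment + 16 weeks follow-up = 36 weeks, as Section 3.2 states.

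**Last dose to last test**

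- Final visit: Day 113 + 16 × 7 = Day 225.
- Interval: 225 − 106 = 119 days = 17.0 weeks.

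**Window and gap**

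- Five months: 5 × 365.25 / 12 = 152.2 days = 21.7 weeks.
- Gap: 152 − 119 = 33 days = 4.7 weeks, or 33 / 152 = 22% of the window.

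**How far the gap depends on the reading**

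- Calendar months (150 to 153 days): 31 to 34 days.
- Months of 28 days (140 days): 140 − 119 = 21 days.
- Final visit 7 days late: 152 − 126 = 26 days. Seven days early: 152 − 112 = 40 days.
- Table 5 header read from the last dose: 16 × 7 = 112 days, so the nominal gap is 152 − 112 = 40 days.

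The gap stays positive under every reading.

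**Who is affected**

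- Early leavers (Section 6.3.1): an ET visit on the last dosing day gives 112 days of follow-up and a gap of about 40 days; an ET visit one week after the last dose gives 119 and 33.
- Subjects who stop IP but stay to Week 32: they are covered if the last dose is on or before Day 225 − 152 = Day 73. A last dose at Week 10 (Day 71) gives 225 − 71 = 154 days, so no gap. A last dose at Week 11 (Day 78) gives 147 days, a gap of about 5 days.

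**Monthly review of abstinence.** Week 24 − Week 16 = 8 weeks, and Week 32 − Week 24 = 8 weeks. No contact is scheduled between these visits, so a monthly review has no place in Table 5.

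**The case against.** The strongest reply is that there is no contradiction. A reporting duty may outlast active testing, and no section promises tests or contacts to 5 months. That is right as far as it goes: this is a shortfall in ascertainment, not two rules that cannot both be obeyed.

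Second, the expected number of pregnancies is small. Criterion 8 asks for contraception with a failure rate below 1% per year. Suppose, as a deliberate overstatement, that all of about 150 active-arm subjects were women of childbearing potential: 150 × 0.01 × 33 / 365 = 0.14 pregnancies would begin in the gap, or about 0.7 at an assumed 5% per year. True numbers would be lower at the same rates; the documents do not give the share of such women. This limits the weight of the point without removing it.

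Third, Section 1.3.2 bases the 16-week follow-up on mean half-lives of 16.4 to 26.7 days. At 119 days after the dose that is 119 / 16.4 = 7.3 to 119 / 26.7 = 4.5 half-lives. This explains the length of follow-up. It does not explain why the pregnancy window is longer, and taking the upper half-life alone would not be a fair argument against the schedule.

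Fourth, the monthly review concerns only subjects relying on true abstinence. Criterion 8b does not say clearly how long it continues, and nothing prevents a site from doing it by telephone. So what is missing there is a stated provision.

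Two stronger readings should be set aside:

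- A reader might infer that pregnancy outcomes will go unfollowed. The documents do not support that: Sections 10.4 and 10.4.1 keep the duty to report a known pregnancy and follow it to completion, and Sections 10.1 and 10.5 keep suspected related serious events reportable at any time.
- A reader might infer that 8-weekly tests in Table 5 breach the 4-weekly rule in Table 4, footnote c. That footnote belongs to the treatment-period schedule and does not govern follow-up.

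**Conclusion.** The point holds as a gap in planned ascertainment. For subjects dosed through Week 15, about the last 33 of 152 days of the window have no scheduled test or contact (26 to 40 days with the final-visit window; nominally about 40 if the 16 weeks run from the last dose). Detection in that period depends on the subject volunteering the information. The absence of a planned contact for monthly abstinence review is a separate, lesser inconsistency.

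The size rests on months of average calendar length, the Week 15 dose being given on schedule, and follow-up starting from the EOT visit. The number of pregnancies affected cannot be estimated from the documents. Neither the primary nor the key secondary analyses at Week 16 are touched. The point is worth correcting because it concerns a safety obligation that the protocol sets for itself and the correction is cheap. This review takes no position on which post-dose duration is right.

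**What to change.** Reconcile Section 4.2 (criterion 8), Table 5, Section 6.3.1, Section 10.1 and Section 10.4.1 so that scheduled pregnancy ascertainment covers whatever post-dose window the sponsor keeps. In doing so, state whether the 16 weeks in the Table 5 header run from the EOT visit or from the last dose.

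If the 5-month window stays:

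- Add one remote contact, for women of childbearing potential only, at the end of the window, and record pregnancy status on the case report form.
- Extend pregnancy ascertainment to that date, including for early leavers, and align the recording period in Section 10.1 for abnormal pregnancy outcomes.
- State how, and for how long, the monthly review of abstinence is carried out and documented during follow-up.

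The cost is amendment wording and a few telephone contacts, with no added clinic visit. The closing contact would fall near Day 106 + 152 = Day 258, about study Week 36.7, so data closure for these subjects moves about 5 weeks later and the end of trial could move with it. The primary database lock, projected in Section 3.1 for after all subjects complete Week 16, is unaffected.
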